4.1.2.2. Exclusion Criteria for Healthy Adults

Participants who meet any of the following criteria at the screening visit (Day 0) or at Day 1, unless noted otherwise, will be excluded from the study:

1. Known close contact with anyone with laboratory-confirmed SARS-CoV-2 infection or COVID-19 within 2 weeks prior to vaccine administration or any known history of SARS-CoV-2 infection or positive SARS-CoV-2 test.
2. Is pregnant or breastfeeding.
3. Is acutely ill or febrile 24 hours prior to or at the screening visit (Day 0). Fever is defined as a body temperature $\geq 38.0^{\circ}\text{C}/\geq 100.4^{\circ}\text{F}$. Participants who meet this criterion may have visits rescheduled within the relevant study visit windows. Afebrile participants with minor illnesses can be enrolled at the discretion of the investigator.
4. Has prior or planned administration of a coronavirus vaccine (eg, SARS-CoV-2, SARS-CoV, or MERS-CoV vaccine).

5. Has current treatment with investigational agents for either prophylaxis against COVID-19 or treatment of COVID-19 (eg, anti-SARS-CoV-2 monoclonal antibodies).
6. Has a medical, psychiatric, or occupational condition that may pose additional risk as a result of participation or that could interfere with safety assessments or interpretation of results according to the investigator's judgment.
7. Has a history of a diagnosis or condition that, in the judgment of the investigator, may affect study endpoint assessment or compromise participant safety, specifically:
 - Active infection at the time of consent
 - Bleeding disorder that is considered a contraindication to IM injection or phlebotomy
 - Dermatologic conditions that could affect local solicited AR assessments
 - Known or suspected allergy or history of anaphylaxis, urticaria, or other significant AR to the vaccine or its excipients
 - Current or previous diagnosis of immunocompromising condition, immune-mediated disease, or other immunosuppressive condition.
8. Has received:
 - Any nonstudy vaccine within 28 days before or after any dose of vaccine (except for seasonal influenza vaccine, which is not permitted within 14 days before or after any dose of vaccine)
 - Intravenous blood products (red blood cells, platelets, immunoglobulins) within 3 months prior to Day 1
 - Systemic immunosuppressants or immune-modifying drugs for >14 days in total within 6 months prior to Screening (for corticosteroids \geq 20 mg/day of prednisone equivalent)
9. Participated in an interventional clinical study within 28 days prior to Day 0 or plans to donate blood products while participating in this study.
10. Is an immediate family member or has a household contact who is an employee of the research center or otherwise involved with the conduct of the study.

4.2. Study Eligibility Criteria (Part B)

4.2.1. Inclusion Criteria (Group B2, Group B3, Group B4, and Group B5)

1. a. Participants must have been previously enrolled in the mRNA-1273-P304 study, are actively participating in Part A and are at least 4 months from the last dose, or
b. Is an adult male or female individual, at least 18 years of age at the time of signing informed consent, is EITHER a kidney or a liver (single organ) transplant recipient who

is at least 90 days after transplantation at the time of consent AND who completed primary vaccination series (3 doses for mRNA COVID-19 vaccine; 2 doses for non-mRNA COVID-19 vaccine or at least 1 dose of non-mRNA combined with 1 dose of mRNA COVID-19 vaccine) under the EUA who are at least 4 months from the last dose. All primary COVID-19 vaccination series must be completed after transplant.

2. Female participants of childbearing potential may be enrolled in the study if the participant has a negative pregnancy test on the day of the booster dose injection (BD-Day 1).

4.2.2. Exclusion Criteria (for Participants who Completed Primary Vaccine Series under EUA) (Group B4)

Exclusion Criteria in Part A will apply except prior or planned administration of a coronavirus vaccine and current treatment with investigational agents for either prophylaxis against COVID 19.

4.3. Lifestyle Restrictions

Participants must not eat or drink anything hot or cold within 10 minutes before oral temperature is taken.

4.4. Screen Failures

Screen failures are defined as participants who consent to participate in the clinical study but are not subsequently given dose 1 of study vaccine and are not allowed to continue to participate in the study. A minimum set of screen failure information is required to ensure transparent reporting of screen failures to meet the Consolidated Standards of Reporting Trials publishing requirements and to respond to queries from regulatory authorities. Minimum information includes date of informed consent, demography, reason(s) for screen failure, eligibility criteria, and information on any SAE that may have occurred from Day 1 to the time of withdrawal.

5. STUDY TREATMENT

5.1. Investigational Product Administered

The term vaccine refers to 100 µg mRNA-1273 primary series vaccine and 100 µg mRNA-1273 BD vaccine in this study. Each dose, regardless of the regimen (single-dose, 2-dose, or 3-dose 100 µg mRNA-1273), administered in the study will be 100 µg mRNA-1273. No placebo will be administered during this study.

The mRNA-1273 vaccine is an LNP dispersion of an mRNA encoding the prefusion stabilized S protein of SARS-CoV-2, formulated in LNPs composed of 4 lipids (1 proprietary and 3 commercially available): the proprietary ionizable lipid SM 102; cholesterol; 1,2 distearoyl sn glycero-3 phosphocholine; and 1-monomethoxypolyethyleneglycol-2,3-dimyristylglycerol polyethylene glycol 2000. Vaccine is provided as a sterile liquid for injection, white to off-white dispersion in appearance, at a concentration of 0.2 mg/mL in 20 mM Tris buffer containing 87 mg/mL sucrose and 10.7 mM sodium acetate at pH 7.5.

5.2. Randomization and Stratification

This is an open-label, single treatment study: there is no randomization. An interactive response technology system will be used to sequentially assign a unique participant identification number within each cohort of the study (transplant recipient cohort or healthy comparison cohort).

Approximately 240 adult participants (220 unvaccinated or previously vaccinated participants who received two 100 µg doses of the Moderna COVID-19 vaccine who have had a kidney or liver transplant and 20 healthy adults) will be enrolled and vaccinated; there will be no stratification or enrollment in blocks. At least 50 SOT recipients who completed primary vaccination series with a non-Moderna COVID-19 under EUA (outside of the mRNA-1273-P304 study) will be enrolled in Part B.

5.3. Dosing and Management of mRNA-1273 Vaccine

5.3.1. Preparation of Study Vaccine for Injection

Each dose of vaccine will be prepared for each participant as detailed in the mRNA1273P304 Pharmacy Manual. For Part A, the volume of vaccine injected will be 0.5 mL, containing a 100 µg dose of mRNA-1273 as detailed in the mRNA-1273-P304 Pharmacy Manual. For Part B, the booster phase, each injection will have a volume of 0.5 mL and contain mRNA-1273 100 µg as in Part A.

5.3.2. Administration of Study Vaccine

Each unvaccinated SOT and Healthy participant (Group A1Group A2, and Group A5) will receive two 100-µg doses of vaccine by IM injection, 28 days apart (ie, Day 1 and Day 29) into the deltoid

muscle, according to the procedures specified in the mRNA-1273-P304 Pharmacy Manual. Preferably, both doses should be administered into the same nondominant arm. Neither dose should be administered into an arm that contains an arteriovenous fistula. Unvaccinated SOT recipients will be offered to receive a third dose of vaccine (Group A2) on Day 85 (56 days after dose 2). Previously vaccinated SOT recipients (Group A3) will receive a single 100- μ g dose (dose 3) on Day 1. In Part B (Group B2, Group B3, Group B4, and Group B5), participants will receive a single 100- μ g dose on BD-D1. Under Amendment #4, unvaccinated SOT participants who will be enrolled will be given 3 100 μ g doses in Part A then proceed to Part B to receive a 100 μ g booster dose. Under Amendment #4, SOT participants previously vaccinated with 2 doses of Moderna COVID-19 vaccine outside of the study who will be enrolled will receive a third 100 μ g dose in Part A then proceed to Part B to receive a 100 μ g BD.

At each visit when vaccine is administered, participants will be monitored for a minimum of 30 minutes after administration. Assessments will include vital sign measurements and monitoring for local or systemic ARs.

Eligibility for a subsequent dose of vaccine will be determined by following the criteria outlined in [Section 6](#).

The study sites will be appropriately staffed with individuals with basic cardiopulmonary resuscitation training/certification. Either onsite resuscitation equipment and personnel or appropriate protocols for the rapid transport of participant to a resuscitation area or facility are required.

5.3.3. Study Vaccine Delivery and Receipt

The Sponsor or designee is responsible for the following:

- Supplying the vaccine
- Confirming the appropriate labeling of the vaccine, so that it complies with the legal requirements of the United States

The investigator is responsible for acknowledging the receipt of the vaccine by a designated staff member at the study site, including the following:

- Confirming that the vaccine was received in good condition
- Confirming that the temperature during shipment from the Sponsor to the investigator's designated storage location was appropriate
- Confirming that the Sponsor has authorized the vaccine for use

- Ensuring the appropriate dose level of vaccine is properly prepared using aseptic technique

Further description of the vaccine and instructions for the receipt, storage, preparation, administration, accountability, and destruction of the vaccine are described in the mRNA-1273-P304 Pharmacy Manual.

5.3.4. Study Vaccine Packaging and Labeling

The Sponsor will provide the investigator (via the study site pharmacy) with adequate quantities of vaccine. The sterile vaccine is packaged in 10R glass vials with a 6.3-mL or 8.0-mL fill volume. The vaccine will have all required labeling per regulations and will be supplied to the pharmacy in an unblinded manner.

The vaccine will be packaged and labeled in accordance with the standard operating procedures of the Sponsor or of its designee, Code of Federal Regulations (CFR) Title 21, Good Manufacturing Practice guidelines, International Council for Harmonisation (ICH) GCP guidelines, guidelines for Quality System Regulations, and applicable regulations.

5.3.5. Study Vaccine Storage

The Moderna COVID-19 vaccine vials are to be stored in a secure area with limited access and protected from moisture and light until it is prepared for administration ([Section 5.3.1](#)). Vials are to be stored frozen between -25°C and -15°C (13°F and 5°F). Unpunctured vials may be stored between 8°C and 25°C (46°F and 77°F) for up to 12 hours. The refrigerator should have automated temperature recording and a 24-hour alert system in place that allows for rapid response in case of refrigerator malfunction. There must be an available backup refrigerator. The refrigerators must be connected to a backup generator. In addition, vaccine accountability study staff are required to keep a temperature log to establish a record of compliance with these storage conditions.

The study site is responsible for reporting any vaccine that was not temperature controlled during shipment or during storage. Such vaccine will be retained for inspection by the monitor and disposed of according to approved methods.

5.3.6. Study Vaccine Accountability and Disposal

It is the investigator's responsibility that the vaccine accountability study staff maintain accurate records in a vaccine accountability log of receipt of all vaccine, study site vaccine inventory, vaccine dispensing, vaccine injections, and return to the Sponsor or alternative disposition of used and unused vaccine vials.

A study site monitor will review vaccine accountability during study site visits and at the completion of the study during onsite and/or remote monitoring visits.

Vaccine may be destroyed at the study site only if permitted by local regulations and authorized by the Sponsor. A certificate of destruction must be completed and sent to the Sponsor or designee.

Additional details are found in the mRNA-1273-P304 Pharmacy Manual.

5.4. Study Treatment Compliance

All doses of vaccine will be administered at the study site under direct observation of medically qualified study staff and appropriately recorded (date and time) in the eCRF. Qualified study site staff will confirm that the participant has received the entire dose of vaccine. If a participant does not receive vaccine or does not receive all of the planned doses, the reason for the missed dose will be recorded. Data will be reconciled with study site accountability records to assess compliance.

Participants who miss the second or third dose due to noncompliance with the visit schedule and not due to a safety pause will still be required to follow the original visit and testing schedule as described in the protocol and their regimen schedule. Unless consent is withdrawn, a participant who withdraws or is withheld from receiving the second or third dose will remain in the study and complete all safety and immunogenicity assessments required through the participant's last scheduled study visit.

The study site staff are responsible for ensuring that participants comply with the allowed study visit windows. If a participant misses a visit, every effort should be made to contact the participant and complete a visit within the defined visit window ([Section 10.1](#)). If a participant does not complete a visit within the time window, that visit will be classified as a protocol deviation. The participant will continue with subsequent scheduled study visits. All safety requirements of the missed visit will be captured and included in the subsequent visit.

5.5. Prior and Concomitant Medications

5.5.1. Prior Medications and Therapies

Information about prior medications (including any prescription or over-the-counter medications, vaccines, or blood products) taken by the participant within the 28 days before providing informed consent (or as designated in the inclusion/exclusion requirements) will be recorded in the participant's eCRF. In addition, for previously vaccinated participants, the 2 previous doses of the Moderna COVID-19 vaccine received prior to signing the informed consent will be recorded in the participant's eCRF regardless of the timing.

For SOT recipients, all immunosuppressant medications will be recorded in the eCRF page, 3 months prior to Screening and throughout the study. Any change in the maintenance therapy should be recorded and the reason for the change documented. Changes include any adjustments (temporarily or permanently), addition of new immunosuppressants, or switching from 1

maintenance rejection prophylaxis regimen to another. Reasons for change may include, but are not limited to, per center protocol, drug interaction, toxicity, or treatment or prevention of graft rejection.

5.5.2. Concomitant Medications and Therapies

At each study visit and each safety telephone call, study site staff must question the participant regarding any medications taken and vaccinations received by the participant and record the following information in the eCRF:

- All immunosuppressant medications, including but not limited to, glucocorticoids (eg, prednisolone), immunophilin binding agents (eg, calcineurin inhibitors, mTOR inhibitors), and inhibitors of de novo nucleotide synthesis (eg, mycophenolic acid, mizoribine, leflunomide, azathioprine) for 3 months prior to Screening and throughout the study. Any immunosuppressants listed in the exclusion criteria if taken during the study should also be recorded.
- All nonstudy vaccinations administered within the period starting 28 days before the first dose of study vaccine, including seasonal influenza vaccine administered for the current influenza season (typically October through April in the Northern Hemisphere).
- All concomitant medications and nonstudy vaccinations taken through 28 days after each dose of study vaccine. Antipyretics and analgesics taken prophylactically (ie, taken in the absence of any symptoms in anticipation of an injection reaction) will be recorded as such.
- Any concomitant medications relevant to or for the treatment of an SAE or MAAE.
- Any concomitant medications used to prevent or treat COVID-19 or its symptoms.
- Participants will be asked in the eDiary if they have taken any antipyretic or analgesic to treat or prevent fever or pain within 7 days after each dose of vaccine, including the day of injection. Reported antipyretic or analgesic medications should be recorded in the source document by the study site staff during the post-injection study visits or via other participant interactions (eg, telephone calls).

Concomitant medications (including vaccinations) will be coded using the WHO Drug Dictionary. If a participant takes a prohibited drug therapy, the investigator and the contract research organization's (CRO's) medical monitor will make a joint decision about continuing or withholding further injection of the participant based on the time the medication was administered, the drug's pharmacology and pharmacokinetics, and whether use of the medication will

compromise the participant's safety or interpretation of the data. It is the investigator's responsibility to ensure that details regarding the concomitant medications are adequately recorded in the eCRF.

5.5.3. Concomitant Medications and Vaccines that May Lead to the Elimination of a Participant from Per-Protocol Analysis

The use of the following concomitant medications and/or vaccines will not require withdrawal of the participant from the study, but may determine a participant's eligibility to receive a second or third dose or evaluability in the PP analysis (analysis sets are described in [Section 8.2](#)):

- Any investigational or nonregistered product (drug or vaccine) other than the mRNA-1273 vaccine used during the study period
- Any medications listed in the study exclusion criteria ([Section 4.1.1.2](#) and [Section 4.1.2.2](#))
- Immunoglobulins and/or any blood products administered during the study period

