- Dermatologic conditions that could affect local solicited AR assessments
- Known or suspected allergy or history of anaphylaxis, urticaria, or other significant AR to the vaccine or its excipients
- Known human immunodeficiency virus infection

8. Has received:

- a. Any nonstudy vaccine within 28 days before or after any dose of vaccine (except for seasonal influenza vaccine, which is not permitted within 14 days before or after any dose of vaccine)
- b. Intravenous blood products (red blood cells, platelets, immunoglobulins) within 3 months prior to Day 1
- c. Therapies that have depleting properties on T-cells, B-cells, and plasma cells (examples of depletion therapies include, but are not limited to, antithymocyte globulin, monoclonal antibodies, and proteosome inhibitors) within the last 3 months prior to enrollment

9. Participated in an interventional clinical study within 28 days prior to Day 0 or plans to donate blood products while participating in this study.

10. Is an immediate family member or has a household contact who is an employee of the research center or otherwise involved with the conduct of the study.

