18. Trained study site personnel will call all participants to collect information relating to any AEs, MAAEs, SAEs, AESIs, AEs leading to discontinuation from dosing and/or study participation (withdrawal), information on concomitant medications associated with those events, and any nonstudy vaccinations. In addition, study personnel will collect information on known participant close contact exposure to someone with known COVID-19 or SARS-CoV-2 infection and on participant experience of COVID-19 symptoms.
19. All concomitant medications and nonstudy vaccinations will be recorded through 28 days after each injection; all concomitant medications relevant to or for the treatment of an SAE, confirmed (biopsy-proven) or suspected events of organ transplant rejection, or MAAE will be recorded from Day 1 through the final visit (Day 394).
20. All immunosuppressant medications, for 3 months prior to Screening and throughout the study. Any change in the maintenance therapy should be recorded and the reason for the change documented.
21. Additional safety calls every 4 weeks should be scheduled if the last dose was delayed and there is a gap beyond 28 days between the safety call scheduled on D377 and the last study visit.

Table 8: Primary Schedule of Events for Unvaccinated Participants Who Receive the 3-Dose Vaccination Regimen (Part A: Group A2)

Visit Number	0	1	2	3	4	5	6	7	8	-	9	-	10		
Type of Visit	C	C	C	C	C	C	C	C	SFU		C	SFU		C	
Month Timepoint		M0		M1		M2	M3		M4	eDiary	SC	M9	eDiary	SC	M15
Study Visit Day	D0 ¹ (Screening)	D1 (Baseline)	D8 ²	D29 ³	D36 ^{2,3}	D57 ^{2,3}	D85 ^{2,3}	D92	D113 ^{2,3}	Every 4 weeks D127 – D239 ^{3,4}	Every 4 weeks D141 – D253 ^{3,5}	D265 ^{2,3}	Every 4 weeks D279 – D419 ^{3,4}	Every 4 weeks D293 – D433 ^{3,5}	D450 ^{2,3}
Window Allowance (Days)	-7		+3	-3/+7	+3	-3	-3/+7	+3	-3/+7	±2	±3	±14	±2	±3	±14
Days Since Most Recent Injection	-	0	7	28/0	7	28	56/0	7	28	-	-	180	-	-	365
Informed consent form, demographics, concomitant medications, medical history	X														
Review of inclusion and exclusion criteria	X	X													
Physical examination including height and weight ⁶	X	X		X		X	X		X			X		X	
Lymph node assessment ⁷		X	X	X	X		X	X							
Vital signs ⁸	X	X		X		X	X		X			X		X	
Pregnancy test ⁹	X	X		X		X									
Blood and urine sampling for safety assessments ¹⁰		X	X	X	X	X	X	X	X						
Recording of standard-of-care kidney or liver laboratory -related AEs ¹¹										X	X	X	X	X	X

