### **6.4. Immunogenicity Analysis**

Immunogenicity samples will be collected at baseline and post-baseline visits, as described in the Schedule of Events in Appendix 1 of Protocol Amendment 4. The PP Immunogenicity Set (Part A/Part B) is the primary analysis population used in the immunogenicity analyses, unless otherwise specified. The mITT set (Part A/Part B) will be used for sensitivity analyses. Concomitant medications and/or vaccines received during the study as described in Section 5.5.3 in Protocol Amendment 4 and Protocol Clarification Memorandum 11 as well as antiretroviral treatments that impact neutralizing antibody responses may be used to determine subject's immunogenicity samples that are eligible for the immunogenicity analyses. Participants will be summarized according to participant group as defined in [Section 6.1](#).

Confidential

The GM levels will be calculated using the following formula:

$$10^{\left\{ \frac{\sum_{i=1}^n \log_{10}(t_i)}{n} \right\}}$$

where  $t_1, t_2, \dots, t_n$  are  $n$  observed immunogenicity levels.

The GMFR measures the changes in immunogenicity levels within subjects. The GMFR will be calculated using the following formula:

$$10^{\left\{ \frac{\sum_{i=1}^n \log_{10}\left(\frac{v_{ij}}{v_{ik}}\right)}{n} \right\}} = 10^{\left\{ \frac{\sum_{i=1}^n \log_{10}(v_{ij}) - \log_{10}(v_{ik})}{n} \right\}}$$

where, for  $n$  subjects,  $v_{ij}$  and  $v_{ik}$  are observed immunogenicity levels for subject  $i$  at time points  $j$  and  $k$ ,  $j \neq k$

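### Immunoglobulins and blood products have no study-long recording requirement unless tied to an SAE, MAAE, rejection or COVID-19, so the section 5.5.3 evaluability rule cannot be fully applied to late and pre-booster samples

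*Protocol*

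**What the plan says.** **Analysis side.** Protocol section 5.5.3 lists exposures that do not force withdrawal but can affect further dosing or per-protocol evaluability. One is "Immunoglobulins and/or any blood products administered during the study period", with no time limit inside the study. SAP section 6.4 refers to section 5.5.3, and to a Protocol Clarification Memorandum 11, as a possible basis for choosing the "immunogenicity samples that are eligible for the immunogenicity analyses".

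**Recording side.** The general rule in section 5.5.2 covers "All concomitant medications and nonstudy vaccinations taken through 28 days after each dose of study vaccine". The schedule repeats it in footnote 19 of Tables 7 and 8: "All concomitant medications and nonstudy vaccinations will be recorded through 28 days after each injection". Table 9 footnote 18 and Table 10 footnote 17 set the same limit for a single injection. SAP section 6.2.5 also defines concomitant medications by 28 days after an injection.

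**Streams without the 28-day limit.** For safety events, section 5.5.2 also requires "Any concomitant medications relevant to or for the treatment of an SAE or MAAE". A separate line, on infection, asks for "Any concomitant medications used to prevent or treat COVID-19 or its symptoms". The section further requires all immunosuppressants throughout the study, adding "Any immunosuppressants listed in the exclusion criteria if taken during the study should also be recorded". The same footnotes add medications for suspected or confirmed rejection, to the final visit.

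**Look-backs.** Section 5.5.1 names blood products in a 28-day pre-consent history, or a longer period where the eligibility criteria set one. Exclusion criterion 8 for transplant recipients bars "Intravenous blood products (red blood cells, platelets, immunoglobulins) within 3 months prior to Day 1". Section 4.2.2 carries the Part A exclusions into Part B for Group B4 only.

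**The concern.** An analysis rule needs the data to apply it. Section 5.5.3 looks at the whole study period, while the recording rule looks at 28 days after each dose plus certain event-linked use. Whatever falls between the two is invisible at analysis, and a product that was never entered cannot be recovered by the statisticians later.

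Passively acquired antibody would be read by the neutralizing and binding assays as the participant's own. In a 6- or 12-month sample it would look like persistence, which is a Part A secondary objective. In a pre-booster sample it would raise one of the two seroresponse baselines in SAP section 6.4.3.1, and so tend to lower the fold rise and seroresponse measured from it. The direction of error therefore differs by endpoint.

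**Working it through.** The plan states no figure on this point, so there is nothing to reproduce. The check counts study days outside the general recording window at target visit days.

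**Inputs.** Dose and sample days come from Protocol Tables 7 to 10; the alternative B5 booster day (Day 129) comes from section 3.1.1. A dose on day d covers days d to d + 28.

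**Days outside the window up to each late sample** = sample day − covered days.

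| Group | Covered days | 6-month sample | 12-month sample |
|---|---|---|---|
| A1, A5 | D1–D57 = 57 | 209 − 57 = 152 | 394 − 57 = 337 |
| A2 | D1–D57 and D85–D113 = 57 + 29 = 86 | 265 − 86 = 179 | 450 − 86 = 364 |
| A3 | D1–D29 = 29 | 180 − 29 = 151 | 365 − 29 = 336 |
| Part B | BD-D1 to BD-D29 = 29 | 181 − 29 = 152 | none planned |

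**Days outside the window before the booster** = (booster day − 1) − last covered day. The last column subtracts 28 on the assumption that the section 5.5.1 look-back is applied again at booster consent on BD-D1.

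| Group | Booster day | Uncovered | With look-back |
|---|---|---|---|
| B2 | D205 | 204 − 113 = 91 | 63 |
| B3 | D120 | 119 − 29 = 90 | 62 |
| B5 | D149 (Table 10) | 148 − 57 = 91 | 63 |
| B5 | D129 (section 3.1.1) | 128 − 57 = 71 | 43 |

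**28-day samples.** Day 57 after two doses, Day 113 after three, Day 29 in A3 and BD-D29 all fall on the last covered day, so the interval since the last dose is fully covered at target. Visit allowances can run past it, by up to 14 days at BD-D29.

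**Do the other streams close the gap?** In every interval above, use for an SAE, MAAE, rejection or COVID-19 is still recorded. Section 7.5.4 defines an MAAE by an unscheduled visit to a healthcare practitioner. The schedules stop recording unsolicited AEs at Day 57 (A1, A5), Day 113 (A2), Day 29 (A3) and BD-D29. After that, replacement immunoglobulin or an elective transfusion given at a planned transplant appointment need not generate an event or a medication entry. The schedule marks the concomitant-medication row at every visit, but its footnote restores the 28-day limit. Staff ask about medications at every contact (sections 5.5.2 and 7.5.8), but section 5.5.2 then lists what is to be entered in the eCRF.

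**The case against.** The case for leaving the text alone has real weight.

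- **Event-linked use is recorded throughout.** Worsening of a chronic condition counts as an AE, and an unscheduled visit for it makes it an MAAE. The safety-call script also asks about medications linked to adverse events. This stands, and confines the gap to planned or non-event use.
- **Entry criteria shrink that group.** Hypogammaglobulinemia is named among the excluded complications of immunosuppression, and intravenous blood products within 3 months are excluded at entry and again for B4. This stands, but neither criterion governs what happens after entry, and B2, B3 and B5 are not rescreened.
- **The rules are permissive.** Both section 5.5.3 and SAP section 6.4 say only that such exposures can be used, and the per-protocol immunogenicity sets already remove major deviations that affect immune response. This stands, but any of these judgements needs the exposure to be known.
- **Boosted participants leave the Part A schedule.** Target booster days (D205, D120, D149) precede the matching 6-month draws (D265, D180, D209), so those boosted on schedule give no Part A 6- or 12-month sample. This stands. The late Part A samples come from a smaller group than total enrolment suggests.
- **Other documents may settle it.** Clarification Memorandum 11 and the eCRF are not available here, and SAP section 6.2.5 lists concomitant procedures, which might capture transfusions, without giving a collection period.

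A reader might infer that these products are recorded for 28 days only, or that passive antibody cannot be removed from late or booster titres at all. The documents do not support either: several streams run to the final visit, so exposure cannot be fully identified, which is a weaker statement.

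**Conclusion.** The mismatch is real and minor. The section 5.5.3 rule, and the sample selection in SAP section 6.4 that draws on it, cannot be fully applied to the 6-month, 12-month and BD-D181 samples, or to the pre-booster baseline in B2, B3 and B5. The day counts assume visits at target days; the smaller pre-booster counts also assume that the 28-day look-back is reapplied at booster consent. Whether the eligibility wording in section 5.5.1 lengthens that look-back for participants rolling over is open to argument.

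Three further inferences should be resisted. The primary 28-day titres are not exposed to this gap at target days. The number of participants or samples affected cannot be estimated, because the documents give no rate of use. Nothing in the documents shows that such use would be confined to transplant recipients, so a one-sided bias against the healthy controls is not established. The late titres are secondary (Part A) or exploratory (BD-D181), and no formal hypothesis testing is planned.

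**What to change.** In Protocol section 5.5.2 and the matching footnotes (Tables 7 and 8 footnote 19, Table 9 footnote 18, Table 10 footnote 17), require immunoglobulins and blood products to be recorded with dates from Day 1, or BD-D1 for Group B4, to the final visit, whether or not they relate to an adverse event. The uncovered days above then fall to zero, and the SAP section 6.4 eligibility rule can be applied at every time point.

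The sponsor should state in SAP section 6.4, before database lock, how long after such a product a sample is excluded. The 3-month period in criterion 8 is an entry rule; the documents do not justify it as an analysis washout, so the interval is the sponsor's to set.

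The cost is one recording rule, one SAP sentence, a few more eCRF entries and possibly a few excluded samples. Sites already ask about medications at each visit and call. Sample size is unaffected.
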